3.1. Intergroup Comparison of Descriptive Characteristics of Students

The descriptive characteristics of students in the intervention and control groups (n=84) are presented in Table 1. No significant differences were found between the groups in terms of age, gender, academic grade point average, and pain management self-assessment scores (p>0.05).

Table 1. Descriptive Characteristics of Students

Descriptive Characteristics	Intervention Group \(\overline{X} \pm SS \\ (Min - Max)		Control Group $\overline{X}\pm SS$ (Min – Max)		t	p
Age		9 ± 2.32 0–31)	21.86 ± 1.64 $(20-29)$		0.757	0.125
Pain management self- assessment (0-10 points)	4.52 ± 1.19 (2-7)		4.33 ± 1.05 (2-6)		0.776	0.333
Gender	n	%	n	%	Chi- square	p
Female	31	73.8	27	64.3	0.345	0.891
Male	11	26.2	15	35.7	0.343	
Academic grade point average						
2.00–3.00	21	50	21	50.0	0.001	1.00
3.01–4.00	21	50.0	21	50	0.001	
t: Independent samples t-test, chi-squa	are test					

3.2. Findings Related to the Level of Knowledge About Pediatric Pain Management

According to the pre-test results, there was no significant difference between the intervention group and the control group in terms of pediatric pain management knowledge level (p > 0.05). However, according to the two-way mixed design ANOVA analysis, group effect (F=16.789, p < 0.001, η^2 =0.170), time effect (F=23.251, p<0.001, η^2 =0.221), and group*time interaction (F=27.834, p<0.001, η^2 =0.253) were found to be statistically significant. In particular, the significance of the group*time interaction indicates that the two groups showed different patterns of change in their knowledge levels over time (Table 2).

In the intervention group, a significant increase was observed in students' pediatric pain management knowledge scores. The mean score, which was 78.04 ± 18.79 in the pre-test, increased to 105.92 ± 23.62 in the post-test and was recorded as 92.26 ± 23.40 in the retention

test. The use of different letters (a, b, c) to denote the means obtained at different measurement times indicates statistically significant differences over time. However, in the control group that received education using the self-learning model, the knowledge level scores remained quite close to each other over time, and no significant change was detected (pre-test: 79.33±19.19, post-test: 78.09±14.68, retention test: 77.16±15.94). These findings indicate that the flipped classroom model is more effective than the self-directed learning model in improving knowledge levels in pediatric pain management and ensuring the retention of this knowledge (Figure 1).

Table 2. Pediatric Pain Management Knowledge Level Scores of the Intervention and Control Groups

Pediatric Pain Management	Intervention group (n=44)	Control group (n=44)	Statistic	Group	Time	Group*time interaction	
Knowledge Scale	Mean (SD)	Mean (SD)	Statistic				
Pre-test	78.04 (18.79) ^a	79.33 (19.19) ^a	F	16,789	23,251	27,834	
Post-test (4th week)	105.92 (23.62) ^b	78.09 (14.68) ^a	p	<0.001	<0.001	<0.001	
Retention Test (3rd month)	92.26 (23.40)°	77.16 (15.94) ^a	η^2	0.170	0.221	0.253	

a-c: Different letters indicate statistically significant groups within each column.

F: two-way mixed design analysis of variance; η^2 , partial eta square; SD, standard deviation.

[figure not shown]

Figure 1. Mean Scores of Pediatric Pain Knowledge by Group and Time

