Study Protocol and Statistical Analysis Plan

Official Title:

The Effect of the Flipped Classroom Model on Nursing Students' Pediatric Pain Management Knowledge and Learning Motivation: A Randomized Controlled Trial (FLIPNURSE)

Unique Protocol ID:

ErsoyU-[name]-FC2022

NCT Number:

Pending (to be assigned)

Sponsor/Collaborators:

Faculty of Health Sciences, Burdur Mehmet Akif Ersoy University

Principal Investigator:

[name], Assistant Professor

Version/Date:

Version 1.0 — August 31, 2021

The Effect of the Flipped Classroom Model on Nursing Students' Pediatric Pain Management Knowledge and Learning Motivation: A Randomized Controlled Trial Abstract

Aim

The aim of this study is to evaluate the effect of the flipped classroom model on nursing students' knowledge level and learning motivation in pediatric pain management.

Background

Pain management in children is an important and multidimensional responsibility in nursing. However, the time allocated to pediatric pain and the opportunities for practical application in nursing education programs are limited. The integration of active learning approaches is necessary to increase knowledge and motivation in this area.

Design

This study is a parallel-group, randomized controlled experimental study conducted at a state university in Turkey.

Methods

A total of 84 third-year nursing students were randomly assigned to an intervention (n=42) and control (n=42) group. The intervention group was taught using the flipped classroom model, while the control group was taught using the self-directed learning model. Data were collected at three time points (pre-test, post-test, and 3 months post-intervention) and analyzed using a two-way mixed-design ANOVA.

Results

At baseline, there were no significant differences between the groups in terms of knowledge and motivation levels (p > 0.05). After the training, significant and sustainable increases were observed in both variables in the intervention group (p < 0.001), while no significant changes were observed in the control group.

The group × time interaction was found to be significant for both variables, indicating that the flipped classroom model provides an effective and sustainable contribution to knowledge level and motivation.

Conclusions

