4.1. The Effect of the Flipped Classroom Model on Pediatric Pain Knowledge Level

A statistically significant and sustained increase in the knowledge levels of nursing students regarding pediatric pain management was observed in those who received education through the flipped classroom model. In particular, the high scores in the retention test compared to the pre-test level indicate the sustainability of learning in the long term. This can be attributed to the flipped classroom model's structure, which encourages active student participation, and its provision of application-based learning environments (Liu et al., 2018; Xu et al., 2019).

These results are consistent with the existing literature. The flipped classroom approach has been shown to enhance knowledge levels in nursing and medical education through various studies (Betihavas et al., 2016; Barranquero-Herbosa, Abajas-Bustillo, & Ortego-Maté, 2022; Merrou et al., 2023). Especially in clinical and applied fields, this model, supported by case analyses, problem-based learning, and group discussions, is reported to enable students not only to acquire knowledge but also to develop their abilities to analyze, evaluate, and transfer knowledge (Liu et al., 2018; Xu et al., 2019; Merrou et al., 2023; Alshehri, Levett-Jones, & Pich, 2024).

The learning gains in question are not limited to quantitative increases in knowledge but also reflect cognitive depth. In this context, the findings can also be evaluated within the framework of Bloom's cognitive domain taxonomy. The flipped classroom model contributes to the activation of higher-order cognitive processes such as analysis, synthesis, and evaluation

beyond the levels of knowledge and comprehension (). Similarly, in a study by Paralikar et al. (2022), it was noted that students who participated in the flipped classroom model showed significant development in Bloom's higher cognitive levels and achieved success, particularly in the application and analysis levels. It is stated that this model facilitates students' access to basic knowledge through offline preparation and reinforces their knowledge with higher-order thinking skills in an interactive classroom environment (Paralikar et al., 2022).

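### The retention conclusion is overstated: scores fell significantly from post-test to month 3, the text does not say so, and no between-arm contrast at month 3 is reported

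*Combined protocol and SAP*

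**What the plan says.** The retention claim appears in several places. Section 3.2 credits the flipped model, relative to self-directed learning, with "ensuring the retention of this knowledge". The abstract's Results state that "significant and sustainable increases were observed in both variables" in the intervention group. Section 4.1 says that retention scores above the pre-test level "indicate the sustainability of learning in the long term", and later claims an advantage in keeping knowledge over both the short and the long term. Section 4.2 judges motivation in the same way, against the starting level.

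The data are in Section 3.2 and Table 2. In the intervention arm, "The mean score, which was 78.04 ± 18.79 in the pre-test, increased to 105.92 ± 23.62 in the post-test", and month 3 was "recorded as 92.26 ± 23.40 in the retention" test. The control arm stayed flat: "pre-test: 79.33±19.19, post-test: 78.09±14.68, retention test: 77.16±15.94". The Table 2 footnote reads "a-c: Different letters indicate statistically significant groups within each column", and the text adds: "The use of different letters (a, b, c) to denote the means obtained at different measurement times indicates statistically significant differences over time". The three intervention means carry the letters a, b and c. Table 3 uses the same scheme for motivation.

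Two other places are more cautious. Section 6 claims gains only in the short and medium term. Section 7 says that follow-up covered three months and that long-term effects could not be assessed.

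**The concern.** If post-test carries b and retention carries c, the document's own comparison finds a significant decline between them. The text reports the month-3 value without calling it a fall, then describes the gains as sustained. A reader of the abstract alone would not learn that a large part of the effect had gone by month 3.

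The inferential basis is also weak. Comparing month 3 with pre-test in one arm shows that some gain remains there. It does not estimate the randomised effect at month 3. The group × time interaction does involve both arms, but it is an omnibus test over three time points and does not isolate month 3. Section 2.10 says the analyses were meant to centre on between-group comparisons, yet none is reported for the time point that carries the retention claim.

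**Working it through.** **Group size.** Section 3.1 and the abstract give 84 students (42 per arm), while Tables 2 and 3 print n=44 per arm. The reported effect sizes settle which was analysed. In this design partial η² = F/(F + N − 2) for all three effects. For the knowledge interaction, N=84 gives 27.834/(27.834 + 82) = 0.253, as reported; N=88 gives 27.834/(27.834 + 86) = 0.245. I use 42 per arm.

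**Knowledge, means from Table 2.**

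| | Pre-test | Post-test | Month 3 |
|---|---|---|---|
| Intervention | 78.04 | 105.92 | 92.26 |
| Control | 79.33 | 78.09 | 77.16 |
| Difference | −1.29 | 27.83 | 15.10 |
| Difference net of pre-test | – | 29.12 | 16.39 |

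- Within the intervention arm: gain 105.92 − 78.04 = 27.88; still present at month 3, 92.26 − 78.04 = 14.22; 14.22/27.88 = 51% kept.
- Net of control change: 16.39/29.12 = 56% kept. This is the fairer figure, because it uses both arms.

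**Month-3 difference between arms, knowledge.** SE = √[(23.40² + 15.94²)/42] = √(801.64/42) = 4.37. The 95% CI is 15.10 ± about 8.7, or 6.4 to 23.8 (p = 0.0009). With 44 per arm the half-width would be 8.5. A baseline-adjusted estimate equals 15.10 + 1.29b, where b is the slope on pre-test, so for b between 0 and 1 it lies between 15.10 and 16.39.

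**Is the marked decline plausible?** The fall is 105.92 − 92.26 = 13.66. Its SE needs the within-student correlation r, which is not reported, so I show a range: SE = √(23.62² + 23.40² − 2r × 23.62 × 23.40)/√42.

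| Assumed r | 95% CI for the fall | p |
|---|---|---|
| 0 | 3.3 to 24.0 | 0.011 |
| 0.3 | 5.0 to 22.3 | 0.003 |
| 0.5 | 6.3 to 21.0 | 0.0005 |
| 0.7 | 8.0 to 19.3 | 0.00002 |

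The fall passes 0.05 throughout. Of the values tried, only r = 0 misses the 0.005 threshold printed in Section 2.10. The error term implied by the interaction F is about 160.8, which gives t = 13.66/√(2 × 160.8/42) = 4.94. That t is approximate, because the reported F values and SDs do not agree fully: the average variance is about 348 from the F values and 383 from the SDs.

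**Is the remaining gain also supported?** Yes. Month 3 against pre-test, 14.22, has p = 0.004 even at r = 0.

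**Motivation, means from Table 3.**

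- Intervention 83.61, 120.66, 101.50; control 86.76, 86.40, 85.61.
- Net of control, the effect goes from 37.05 + 0.36 = 37.41 to 17.89 + 1.15 = 19.04, so 19.04/37.41 = 51% is kept.
- The month-3 difference is 101.50 − 85.61 = 15.89, with SE √[(12.26² + 12.36²)/42] = 2.69 and 95% CI about 10.5 to 21.2.
- Section 2.2.3 gives a scale maximum of 120, so a mean of 120.66 cannot occur. Setting it to 120 gives 19.04/(36.39 + 0.36) = 52% kept. That shows little sensitivity to this one figure, but it does not validate the underlying data.

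**The case against.** A reader might infer that the tables contradict the retention claim, or that the benefit was lost. The documents do not support that. The letters that separate post-test from month 3 also separate month 3 from pre-test, so a significant remaining gain is marked as well. Sections 4.1 and 4.2 state their yardstick, the starting level, and on that yardstick text and tables agree. The sentence in Section 3.2 is comparative, and a month-3 difference of 15.10 with a CI excluding zero supports superiority over control.

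Other points for the authors also stand. All means, SDs and letters are printed, so nothing is hidden. The abstract's recommendation rests on improved knowledge and motivation and does not mention retention. Section 6 is worded more modestly. Pre-test knowledge differs by only 1.29, so baseline adjustment would change little there.

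What does not stand is the unqualified wording. Being above pre-test is compatible with losing a large share of the effect, and a reader told that gains are sustainable will not expect that. The long-term claims in Sections 4.1 and 4.2 also conflict with the limitation stated in Section 7.

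**Conclusion.** The retention conclusion is overstated, not contradicted. The data support partial retention at three months: knowledge remains above pre-test and above control, but the between-arm difference falls from 27.83 to 15.10, and about 56% of the effect net of control is kept. The text does not report the decline that its own tables mark as significant.

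The month-3 CI assumes 42 per arm and is unadjusted. Three uncertainties remain. The post hoc test behind the letters is not named. Section 2.8 puts the post-test one month after training while the tables label it week 4, so the interval of decline is about two or three months. The motivation percentage should not be quoted until the mean of 120.66 has been checked. None of these changes the conclusion for knowledge, the primary outcome.

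**What to change.** 1. For each outcome, report the baseline-adjusted between-arm difference at month 3 with its 95% CI, and rest the retention statement on it.
2. Report the change from post-test to month 3 with a 95% CI, and name the post hoc test and any multiplicity adjustment behind the letters.
3. In the abstract and Sections 3.2, 4.1 and 4.2, replace the unqualified wording with: *partly retained at 3 months: scores remained above pre-test and above control, but declined significantly from post-test*.
4. Remove the long-term claims about this trial from Sections 4.1 and 4.2, in line with Section 7.
5. Check the motivation post-test scores against the scale maximum before quoting any percentage, correct the n=44 table headings or explain them, and reconcile the post-test timing.

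The cost is two contrasts per outcome from data already collected, one data check and some rewording. The downside for the authors is a less favourable claim.

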3.3. Findings Related to Motivation Levels

Findings related to students' motivation levels are summarized in Table 3. There was no significant difference in motivation level scores between students in the intervention group and those in the control group in the pre-test (p > 0.05). However, when the results of the two-way mixed design ANOVA were examined, group effect (F=39.206, p < 0.001, η^2 =0.323), time effect (F=67.749, p<0.001, η^2 =0.452), and group*time interaction (F=70.240, p<0.001, η^2 =0.461) were found to be statistically significant. The significance of the group*time interaction indicates that the effect of the time factor on motivation levels is not the same for both groups (Table 3).

In the entrepreneurial group that received education with the flipped classroom model, a significant increase was observed in students' motivation scores. The average score, which was 83.61 ± 12.61 in the pre-test, increased to 120.66 ± 17.20 in the post-test and was recorded as 101.50 ± 12.26 in the retention test. The use of different letters (a, b, c) to denote the averages at different measurement times indicates statistically significant differences over time. In contrast, the motivation level scores of the control group, which received education using the self-learning model, remained quite close to each other at all time points, and no significant change was observed (pre-test: 86.76 ± 12.03 , post-test: 86.40 ± 11.91 , retention test: 85.61 ± 12.36). These findings indicate that the flipped classroom model is more effective than the self-directed learning model in enhancing students' motivation (Figure 2).

Table 3. Learning Motivation Scores of the Intervention and Control Groups

Motivation Survey Regarding Teaching	Intervention group (n=44) Mean (SD)	Control group (n=44) Mean (SD)	Statistic	Group	Time	Group*time interaction
Materials Pre-test	83.61 (12.61) ^a	86.76 (12.03) ^a	F	39,206	67,749	70,240
Post-test (4th week)	120.66 (17.20) ^b	86.40 (11.91) ^a	p	<0.001	<0.001	<0.001
Retention Test (3rd month)	101.50 (12.26)°	85.61 (12.36) ^a	η^2	0.323	0.452	0.461

a-c: Different letters indicate statistically significant groups within each column.

F: Two-way mixed design analysis of variance; η^2 , partial eta square; SD, standard deviation.

[figure not shown]

Figure 2. Mean Scores of Learning Motivation by Group and Time

4. Discussion

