2.2.3. Motivation Questionnaire Regarding Teaching Materials

The Teaching Material Motivation Survey (ÖMMA) was developed by Keller and its validity and reliability were studied in Turkish by Kutu and Sözbilir (Keller, 2006; Kutu & Dir, Sözbilir, 2011). This scale, which aims to determine students' motivation levels toward instructional materials, consists of a total of 24 items on a 5-point Likert scale. The items in the attention-appropriateness dimension of the ÖMMA are 1, 2, 3, 4, 5, 6, 7, 8, 9, 10, and 11; while the items in the confidence-satisfaction dimension are 12, 13, 14, 15, 16, 17, 18, 19, 20, 21, 22, 23, and 24. Five items in the questionnaire (3, 12, 14, 16, 18) were reverse-coded. The minimum score in the questionnaire is 24, and the maximum score is 120. A high score on the survey indicates high motivation regarding the teaching material. The Cronbach's alpha coefficient is 0.83. In this study, the Cronbach's alpha value was found to be 0.789.

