2.3. Sample, randomization, and prevention of bias

The population of this study consisted of a total of 152 third-year nursing students enrolled in the Child Health and Nursing course. Sample size and power analysis were performed using the G*Power 3.1.9 program. Considering the research design (three measurements and two groups), the following parameters were used for the ANOVA test in repeated measurements: $\alpha = 0.05$, power $(1-\beta) = 0.80$, and moderate effect size (f = 0.25). Accordingly, a minimum of 27 participants per group and a total of at least 54 participants were required. Considering potential data losses, the study was conducted with 44 participants in each group (Cohen, 2013; Faul et al., 2009).

Students were divided into two groups using stratified sampling based on their academic achievement levels. Those with an academic grade point average between 2.00 and 3.00 formed the first stratum, while those with a grade point average between 3.01 and 4.00 formed the second stratum. Within each stratum, participants were assigned to either the intervention or control group in equal numbers using a computer-assisted simple random assignment method with blind allocation. The randomization process was conducted by an independent biostatistician not involved in the study, and no blocking randomization or other restriction methods were used.

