2.10. Data analysis

Data analysis was performed using IBM SPSS 25.0 (IBM Corp., Armonk, NY, USA). The assumption of normal distribution was evaluated using the Kolmogorov–Smirnov test and supported by skewness and kurtosis values within the ± 2 range. The internal consistency of the scales was determined using Cronbach's alpha coefficient.

Within the scope of statistical analysis, frequency distributions and descriptive statistics were calculated; independent samples t-test and chi-square test were used for intergroup comparisons. Two-Way Mixed ANOVA was applied to examine the effects of group, time, and group × time interaction on education. All necessary assumptions (e.g., normal distribution,

variance homogeneity, sphericity) were tested and found to be met in this analysis. The significance level was set at p<0.005 for all statistical analyses. Additionally, no subgroup analyses were conducted for variables such as age, gender, or academic achievement. All analyses were designed to focus on between-group comparisons.

3. Results

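### The SDs and F statistics in Tables 2 and 3 contradict each other, one motivation mean exceeds the scale maximum, and three Table 1 p-values do not match their test statistics

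*Combined protocol and SAP*

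**What the plan says.** The analysis in section 2.10 is a two-way mixed ANOVA (group, time, and their interaction) on three measurements in two groups. The same section says of the assumptions: "variance homogeneity, sphericity) were tested and found to be met in this analysis".

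- **Knowledge (primary), section 3.2 and Table 2:** "group effect (F=16.789, p < 0.001, η^2 =0.170), time effect (F=23.251, p<0.001, η^2 =0.221", with an interaction F of 27.834 (partial eta-squared 0.253).
- **Motivation (secondary), section 3.3 and Table 3:** "group effect (F=39.206, p < 0.001, η^2 =0.323), time effect (F=67.749, p<0.001, η^2 =0.452", with an interaction F of 70.240 (0.461). The intervention mean "increased to 120.66 ± 17.20 in the post-test".
- **Motivation scale, section 2.2.3:** "The minimum score in the questionnaire is 24, and the maximum score is 120".
- **Baseline, section 3.1:** "No significant differences were found between the groups in terms of age, gender, academic grade point average, and pain management self-assessment scores (p>0.05". Table 1 prints t=0.757 with p=0.125 (age), t=0.776 with p=0.333 (self-assessment), and chi-square 0.345 with p=0.891 (gender).
- **Group size:** the abstract says "A total of 84 third-year nursing students were randomly assigned to an intervention (n=42) and control (n=42) group", and the Table 1 counts agree. Section 2.3 says "the study was conducted with 44 participants in each group", and the headers of Tables 2 and 3 also give 44.

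**The concern.** Tables 2 and 3 hold the trial's only effect and precision figures for its two outcomes. A mixed ANOVA can be checked from its cell means, SDs and Fs, and these do not fit together for either outcome. A reader who computes a standardised effect or a confidence interval from the SDs uses a different error variance from one who works back from the Fs, and has no basis for choosing between them.

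The motivation mean raises a separate question. Scores bounded at 120 cannot average more than 120, and could average exactly 120 only with an SD of zero. The printed SD is 17.20.

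**Working it through.** **Which n was analysed.** Partial eta-squared equals F/(F+N−2) for all three effects. With N=84, the printed Fs give 0.170, 0.221 and 0.253 (knowledge) and 0.323, 0.452 and 0.461 (motivation), which are the six printed values. With N=88 the group values would be 0.163 and 0.313. All twelve printed means are an integer total divided by 42 and truncated to two decimals. Four of them (105.92, 92.26, 79.33, 86.76) cannot arise from 44 students by rounding or truncation. The analysis therefore used 42 per group.

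**Totals (pre, post, 3 months).**
- Knowledge: intervention 3278, 4449, 3875; control 3332, 3280, 3241.
- Motivation: intervention 3512, 5068, 4263; control 3644, 3629, 3596.

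**What reproduces.** Time and interaction share an error term and degrees of freedom, so F(time)/F(interaction) must equal SS(time)/SS(interaction). For knowledge both are 0.83535. For motivation both are 0.96454.

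**What does not reproduce.** For equal groups with complete data,

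SS(subjects) + SS(error) = (n−1) × ΣSD²

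This is an algebraic identity and needs no assumption about sphericity or the correlation between visits. The left side comes from the means and Fs: MS(subjects) = SS(group)/F(group) on 82 df, and MS(error) = SS(time)/[2·F(time)] on 164 df.

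| | Knowledge | Motivation |
|---|---|---|
| SS(group), SS(time) | 12,138.9; 7,476.1 | 15,463.0; 14,171.2 |
| MS(subjects) | 12,138.9/16.789 = 723.03 | 15,463.0/39.206 = 394.40 |
| MS(error) | 7,476.1/(2×23.251) = 160.77 | 14,171.2/(2×67.749) = 104.59 |
| 82·MS(subjects) + 164·MS(error) | 59,288 + 26,366 = 85,654 | 32,341 + 17,152 = 49,493 |
| 41·ΣSD² | 41×2,296.37 = 94,151 | 41×1,044.50 = 42,824 |
| Ratio | 0.910 | 1.156 |
| Average SD, √(SS/246): from Fs, from SDs | 18.7, 19.6 | 14.2, 13.2 |

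**Explanations tried.**
- Rounding: moving every mean and SD by 0.01 keeps the ratios within 0.908–0.912 and 1.153–1.158.
- 44 per group: 0.953 and 1.211.
- SDs computed with divisor n: 85,654/(42×2,296.37) = 0.888 and 49,493/(42×1,044.50) = 1.128.
- Some other n: the ratio is proportional to n, so knowledge needs 42/0.910 ≈ 46 and motivation 42/1.156 ≈ 36. No single n fits both.

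**Size of the conflict.** The two allocations below are illustrations, not corrected results.
- Keep the SDs and the group F. For knowledge, MS(error) = (94,151−59,288)/164 = 212.58, so the time and interaction Fs are 17.6 and 21.05 (printed 23.3 and 27.8). For motivation, (42,824−32,341)/164 = 63.92 gives 110.8 and 114.9 (printed 67.7 and 70.2).
- Keep the SDs and the time F. For knowledge, MS(subjects) = (94,151−26,366)/82 = 826.65, so the group F is 14.7 (printed 16.8). For motivation, (42,824−17,152)/82 = 313.08 gives 49.4 (printed 39.2).

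The smallest of these, the knowledge group F of 14.7, has p=0.00025, and the knowledge time F of 17.6 has p=1.2e-7.

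**The motivation post-test mean.** The total is 5,068, against a possible 42×120 = 5,040, so it is 28 points over. A misprint is unlikely. Given the other five totals and the printed time F, 5,068 implies an interaction F of 70.240, as printed, while 5,067 gives 70.244 and 5,069 gives 70.235. Nor does this mean explain the SD/F gap. At 120.00 the ratio is still 1.12, and the value that closes it, 117.65, gives F(time)/F(interaction) of about 0.955, not 0.9645.

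**Table 1.**
- Gender: 84×(31×15−11×27)²/(42×42×58×26) = 0.891, p=0.345. The printed pair is reversed.
- Age: t=0.757 on 82 df gives p=0.451, printed 0.125.
- Self-assessment: (4.52−4.33)/√[(1.19²+1.05²)/42] = 0.776, as printed, giving p=0.440, printed 0.333.
- One-sided values (0.226 and 0.220) do not match either.

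**The case against.** No conclusion is overturned. The rebuilt Fs all keep p<0.001, the corrected Table 1 p-values stay above 0.05, and for the primary outcome the gap is about 9% of the error sum of squares. This is true, and it limits the consequence. It does not make the printed effect sizes and SDs usable.

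The knowledge means agree with the ratio of their Fs, so for the primary outcome only the SDs and Fs conflict. That stands. A mean is in doubt only for motivation. There the F ratio shows that 120.66 entered the analysis, provided the other five means are right. It does not show why, and the fault could lie in the data, the scoring or the stated range. The range does fit the 24 five-point items in section 2.2.3.

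For age, the intervention mean is damaged in the text available, so it might be the t that is wrong. However, 21.86 + 0.757×√[(2.32²+1.64²)/42] = 22.19, which agrees with the surviving last digit, 9. The p-value is the likelier error.

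The evidence against the statement on assumptions is weak. The group variance ratio for knowledge at post-test is (23.62/14.68)² = 2.59 (p=0.003), but only this one of six ratios falls below the 0.005 level printed in section 2.10. A variance ratio is not Levene's test, and the SDs are themselves in doubt. This supports asking for the test results and no more.

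**Conclusion.** The concern holds. The SDs and Fs of Tables 2 and 3 cannot both be right: the ratio of F-implied to SD-implied error is 0.91 for knowledge and 1.16 for motivation. The documents do not show whether the SDs, the Fs or both are wrong. The motivation post-test mean is impossible on the stated scale, and that analysis appears to have used totals the scale cannot produce. Three Table 1 p-values do not match their statistics, which is a minor matter of presentation.

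The result assumes 42 per group with complete data at all three visits. The eta-squared values and the means support this, as does the exclusion in section 2.4 of students who did not complete every stage. A PDF reading error is unlikely, because text and tables print the same figures. Significance is unlikely to change. The size and precision of both effects remain unverified until the tables are rerun.

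**What to change.** 1. Rerun Tables 1 to 3 from the locked raw data. State the analysed n, and reconcile the 44 in section 2.3 and the table headers with the 42 in the abstract and Table 1.
2. Check every motivation total against 24 to 120, check item scoring and reverse coding in both groups at all visits, and confirm the stated range.
3. Correct whichever means, SDs, Fs, eta-squared values and p-values prove wrong, in the text as well as the tables.
4. In Table 1, swap the gender chi-square and p-value, and correct the age and self-assessment p-values after confirming the t statistics.
5. Report the Levene and Mauchly results, and keep the statement that assumptions were met only if they support it.

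The cost is one rerun and a set of table corrections; no new data are needed. Some figures may become less favourable. Bringing out-of-range post-test scores down would by itself lower the intervention mean and probably shrink the motivation effect, although a scoring error that also touched the control group or other visits could alter that.
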